3. STUDY OBJECTIVES

3.1 Primary objective

The primary objective is to investigate whether AZD9668 shows evidence of efficacy in bronchiectasis patients by investigation of:

- Absolute and percentage neutrophil cell count in the sputum
- Signs and symptoms of bronchiectasis (including effects on quality of life)

The associated primary outcome variables can be found in Table 1.

Table 1 Primary outcome variables

Outcome Variables	Description
Absolute and percentage neutrophil cell count in sputum	Absolute cell count will be performed and sputum cytospin slides will be produced for assessment of differential cell count
Bronkotest © diary card	The Bronkotest © diary card will be completed by patients from enrolment until follow up visit, to capture signs and symptoms of their bronchiectasis
24 hour sputum collection weight	Patients will be asked to collect sputum for a 24 hour period on 2 occasions during the study
St George's Respiratory Questionnaire	The quality of life questionnaire "St George's Respiratory Questionnaire for COPD patients" (SGRQ-C) will be completed pre treatment and at the end of the treatment period
Lung function tests	The following lung function tests will be assessed at clinic visits 1, 2, 4 and 5. SVC (slow vital capacity), FEV1 (forced expiratory volume in 1 second), FVC (forced vital capacity), forced expiratory flow between 25 and 75% of forced vital capacity (FEF25-75)

3.2 Secondary objectives

The Secondary Objectives are:

- To investigate the effect of AZD9668 on Neutrophil Elastase (NE) activity in sputum
- To investigate the effect of AZD9668 on other inflammatory markers in sputum
- To investigate the effect of AZD9668 on inflammatory markers in blood
- To investigate the safety and tolerability of 28 days' dosing with AZD9668 in bronchiectasis patients
- To confirm AZD9668 exposure in plasma and in spontaneously produced sputum
- To investigate the effect of AZD9668 on urine desmosine (marker of tissue degradation)

The associated outcome variables are detailed in Table 2. The markers assayed will be dependent on the availability of validated methods.

Table 2 Secondary outcome variables

Outcome variables	Description
NE activity in sputum	Spontaneous sputum collections will be processed according to the laboratory manual and aliquots will be collected for NE activity
Inflammatory markers in sputum	Spontaneous sputum collections will be processed according to the laboratory manual and aliquots will be collected for assessment of the following markers (including, but not limited to) – TNF- α , IL-8, LTB-4, IL-6, IL-1 β , RANTES, MCP-1
Inflammatory markers in blood	Blood samples will be collected for assessment of the following markers (including, but not limited to) - Absolute and percentage differential cell count, TNF- α , IL-8, high sensitivity CRP, Amyloid-A, IL-6, IL-1 β
Safety and tolerability of AZD9668	Vital signs, ECG, haematology, clinical chemistry, urinalysis, sputum culture, reported adverse events
Pharmacokinetic parameters (plasma and sputum)	Concentration of AZD9668 in plasma and sputum

Table 2 Secondary outcome variables

Outcome variables	Description
Tissue degradation markers	Urine desmosine will be measured from the 24 hour urine collections

3.3 Exploratory objectives

The Exploratory Objectives are:

- To investigate the effect of AZD9668 on other markers of tissue degradation (plasma desmosine and sputum hydroxyproline)
- To investigate the effect of AZD9668 on markers of mucus hyper-secretion (MUC5AC in sputum)
- To collect samples for possible retrospective pharmacogenetics analysis to investigate the influence of genotype on pharmacokinetics (and pharmacodynamic response where appropriate). This will not form part of the Clinical Study Report (CSR).

4. STUDY PLAN AND PROCEDURES

This Clinical Study Protocol has been subject to a peer review according to AstraZeneca standard procedures.

4.1 Overall study design and flow chart

This is a randomised, double-blind placebo-controlled, parallel group study in 40 randomised patients with Bronchiectasis. It is planned to perform this study in approximately 10 centres across 2 countries; Canada (approximately 6 sites) and UK (approximately 4 sites) with each site randomising 2-6 patients during the study. Additional sites in Europe will be considered as required.

After patients have provided informed consent, they will be enrolled into the study. Patients who complete the study, will be required to attend 10 visits, some of which may be undertaken in their own home. The overall study design is outlined in Figure 1.

Patients will be randomised (1:1) at Visit 2, to receive either AZD9668 or placebo. They will be given sufficient tablets to allow dosing, 60 mg (b.i.d), until Visit 3 (14 days +/-2 days). At Visit 3, the remaining study drug will be dispensed. This will be sufficient to allow 60 mg b.i.d dosing until Visit 4 (day 28 +/-2 days).

Full details of the study assessments taking place at each visit are outlined in Table 3.

Patients should be informed that they should fast on the morning of Visits 2 and 4.

They should also with-hold their morning dose of medication on Visit 4 as it will be taken at clinic following the pre-dose assessments (as outlined in Table 3) and also at Visit 3a and Visit 3b, they should perform their sputum collections prior to taking their study medication.

Specific details of timing of sputum collections and subsequent analyses are outlined in Table 4.

Table 3 Table of study assessments

Study Visit	1	1a	1b	2	2a	3	3a	3b	4	5¹
Timing	Day -21 to Day -8	Within 7 days of Visit 2 ^a	Within 7 days of Visit 2 ^a	Day 1	Day 7 (±2 days)	Day 14 (±2 days)	Within 7 days of Visit 4 ^a	Within 7 days of Visit 4 ^a	Day 28 (±2 days)	7 days (±2 days) after Visit 4
Detail	Enrolment	Sputum/ Urine	Sputum/ Urine	Start of treatment	Interim visit	Interim visit	Sputum	Sputum	End of treatment	Follow up visit
Written informed consent ^b	✓									
Demographics	✓									
Physical examination	✓									✓
Medical/surgical history	✓									
Dispense study drugs				✓		✓				
Safety bloods	✓ ^d			✓ ^c	✓	✓			✓ ^c	✓
Urinalysis	✓			✓ ^c		✓			✓ ^c	✓
Inclusion/exclusion criteria	✓			✓ ^c						
Lung function tests	✓			✓ ^c					✓ ^c	✓
Vital signs	✓			✓ ^e		✓			✓ ^e	✓
ECG	✓			✓ ^e		✓			✓ ^e	✓
Drug accountability						✓			✓	
Bronkotest [®] diary card ^f	✓	✓	✓	✓		✓	✓	✓	✓	✓

Table 3 Table of study assessments

Study Visit	1	1a	1b	2	2a	3	3a	3b	4	5¹
Timing	Day -21 to Day -8	Within 7 days of Visit 2 ^a	Within 7 days of Visit 2 ^a	Day 1	Day 7 (±2 days)	Day 14 (±2 days)	Within 7 days of Visit 4 ^a	Within 7 days of Visit 4 ^a	Day 28 (±2 days)	7 days (±2 days) after Visit 4
Detail	Enrolment	Sputum/ Urine	Sputum/ Urine	Start of treatment	Interim visit	Interim visit	Sputum	Sputum	End of treatment	Follow up visit
Concomitant medications recorded	✓	✓	✓	✓	✓	✓	✓	✓	✓	✓
Adverse event questioning		✓	✓	✓	✓	✓	✓	✓	✓	✓
Pharmacogenetics blood sampling ^g				✓						
Return 24 hr urine collection (for desmosine) ^h		✓ ^h	✓ ^h						✓ ^h	
Return 24 hr sputum collection (for weight) ^h		✓ ^h	✓ ^h						✓ ^h	
Randomisation (AZD9668/placebo)				✓						
Waking sputum sample ^{ij}		✓ ^c	✓ ^c	✓ ^c			✓ ^c	✓ ^c	✓ ^c	
2 hr sputum collection ^{ij}		✓	✓	✓ ^c			✓ ^c	✓ ^c	✓ ^c	
1 to 2 hr post-dose sputum sample ^j									✓	

Table 3 Table of study assessments

Study Visit	1	1a	1b	2	2a	3	3a	3b	4	5 ¹
Timing	Day -21 to Day -8	Within 7 days of Visit 2 ^a	Within 7 days of Visit 2 ^a	Day 1	Day 7 (±2 days)	Day 14 (±2 days)	Within 7 days of Visit 4 ^a	Within 7 days of Visit 4 ^a	Day 28 (±2 days)	7 days (±2 days) after Visit 4
Detail	Enrolment	Sputum/ Urine	Sputum/ Urine	Start of treatment	Interim visit	Interim visit	Sputum	Sputum	End of treatment	Follow up visit
Quantitative sputum culture				✓ ^m						✓
AZD9668 PK sample (blood)				✓ ^c					✓ ^c	
Blood sampling for pharmacodynamic markers ^k				✓ ^c					✓ ^c	
St George's Respiratory Questionnaire				✓					✓	

^a Visit 1a should occur at least 24 hours before Visit 1b.

^b The informed consent should be signed before any study-related procedures, restrictions or screening assessments are performed.

^c Pre-dose

^d To include measurement of FSH (menopausal status) and hCG (pregnancy test) in serum for female patients at Visit 1.

^e Pre-dose and 1-2 hours post dose .

^f Issued at Visit 1 and patient should be instructed to bring it to each clinic visit, for review by site staff. The diary card should be completed daily until termination from the study.

^g Sample should be taken any point after randomisation.

^h Patients should be instructed to start 24 hour collection on rising the day before their scheduled visit. They should collect all sputum/urine for the 24 hour period leading to either Visit 1a **or** Visit 1b and Visit 4.

ⁱ After collecting the waking sputum sample in one pot, patients should collect another sample (of at least 1 to 2 g sputum) in another pot, over a maximum of 2 hours. Immediately after finishing collection of the 2 hour sample, all sputum samples should be taken directly to the clinic or dispatched directly to the local sputum processing lab (dependent on the clinic appointment time and/or patient's preference).

^j Details of all analytes measured in these spontaneous sputum samples can be found in Table 4 .

^k Plasma and serum samples will be collected. See Section 7.6.2.

^l If the patient discontinues after randomisation they should be asked to attend for Visit 5.

^m The aliquot for the quantitative sputum culture will be taken from the waking sample at Visit 2.

Table 4 Spontaneous sputum sample summary

Timing of sample	Visit 1	Visit 1a	Visit 1b	Visit 2 (pre dose)	Visit 2a	Visit 3	Visit 3a	Visit 3b	Visit 4 (pre dose)	Visit 4 (1-2 hours post dose)	Visit 5
Analysis											
Cytospin production		✓ ^b	✓ ^b	✓ ^b			✓ ^b	✓ ^b	✓ ^b	✓	
AZD9668 sputum concentration				✓ ^b					✓ ^b	✓	
Aliquots for pharmacodynamic marker (including inflammatory and mucus hyper-secretion markers)		✓ ^b	✓ ^b	✓ ^b			✓ ^b	✓ ^b	✓ ^b	✓ ^a	
Quantitative sputum culture				✓ ^c							✓ ^c

^a Aliquot for NE activity only

^b Waking sputum sample and 2 hour sputum collection

^c Waking sample only

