5.1 Inclusion criteria

For inclusion in the study patients must fulfil the following criteria.

1. Provision of informed consent prior to any study specific procedures

2. Male, or female of non-child bearing potential (defined as amenorrhoeic for 12 months and follicle stimulating hormone (FSH) plasma concentration within the post-menopausal range as defined by the laboratory) or surgically sterile (defined as having undergone bilateral oophrectomy and/or hysterectomy; tubal ligation on its own is not adequate), between 18 and 80 years
3. Have a clinical diagnosis of idiopathic or post infective bronchiectasis as diagnosed with a historical high resolution computerised tomography (HRCT) or bronchogram
4. Be sputum producers with a history of chronic expectoration on most days of most weeks of the year. Patients should have a history of spontaneously producing an average of 3 ml or more sputum on a daily basis and should be able to provide at least 2 of the 3 required baseline sputum samples
5. Have normal laboratory values at Visit 1, unless the investigator considers an abnormality to be clinically irrelevant

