7.4.1 Efficacy Variables

7.4.1.1 Differential cell count in sputum

Patients will be provided with appropriately labelled pots and instructions to collect spontaneous sputum samples at Visits 1a, 1b, 2, 3a, 3b and 4. On each of these visit days, patients will collect a sputum sample on waking, in one pot. Another sample (of at least 1-2g sputum) should be collected in another pot, over a maximum of 2 hrs. Immediately after finishing collection of the 2 hr sample, all sputum samples should be taken directly to the clinic or dispatched directly to the local sputum processing lab (dependent on the clinic appointment time and/or patient's preference). In addition, patients will be asked to produce a spontaneous sputum sample post-dose (1 to 2 hours) at Visit 4 in the clinic.

The sputum will be processed locally according to the process detailed in the laboratory manual and will result in the production of cytospin slides and aliquots of sputum supernatant. Details of the aliquots of sputum supernatant are covered under pharmacodynamic variables

(Section 7.6.1) and the sputum cytopspins will be used to determine the cell count and differential. N.B. Absolute and percentage neutrophil cell count will be determined and the other differential counts will be reported for completeness.

These cytopspins will be produced locally before being shipped to the analysis lab, to have a differential cell count performed. Details of analysis laboratory, shipping and sample handling can be found in the laboratory manual.

Please refer to Table 3 for further detail around sampling times.

7.4.1.2 24 hour sputum weight

Patients will be provided with appropriately labelled collection pots at Visit 1 and 3, to enable them to collect all sputum produced during a 24 hour period at Visit 1a or 1b and Visit 4.

Patients should be instructed to collect the sputum from the morning prior to the scheduled visit for a full 24 hour period. This complete collection will be sent, or brought to site (as agreed, in advance, with staff and patient), weighed by the site staff and the weight recorded in the pCRF.

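### When a sampling visit falls the day before the visit that ends a 24-hour sputum collection, the 2-hour sample is diverted from it, and a primary variable may be under-measured at one time point only

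*Protocol*

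**What the plan says.** The weight of the 24-hour sputum collection is one of the primary outcome variables (Protocol, Section 3.1, Table 1): "Patients will be asked to collect sputum for a 24 hour period on 2 occasions during the study". Section 12.2.2 makes the change from baseline to Visit 4 its primary analysis.

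Table 3, footnote h fixes the collection window: "Patients should be instructed to start 24 hour collection on rising the day before their scheduled visit". It continues: "They should collect all sputum/urine for the 24 hour period leading to either Visit 1a", with Visit 1b as the alternative at baseline and Visit 4 as the second occasion.

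The visits that may fall inside that window are spaced as follows:
- **Visits 1a and 1b.** Footnote a says "Visit 1a should occur at least 24 hours before Visit 1b".
- **Visits 3a and 3b.** The timing row says only "Within 7 days of Visit 4". The columns carry the same footnote mark, but its text names only Visits 1a and 1b.

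On each of Visits 1a, 1b, 2, 3a, 3b and 4 the patient also gives spot samples. Section 7.4.1.1 says "On each of these visit days, patients will collect a sputum sample on waking, in one pot", and footnote i says "After collecting the waking sputum sample in one pot, patients should collect another sample (of at least 1 to 2 g sputum) in another pot", with a limit of 2 hours. These pots then go straight to the clinic or the local processing laboratory. Section 7.4.1.2 has site staff weigh the 24-hour collection and does not mention the other pots.

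**The concern.** The two sets of instructions can claim the same sputum. On the first morning of a 24-hour collection, everything produced after rising belongs in the collection pot. If that morning is also a Visit 1a or Visit 3b morning, at least 1 to 2 g of it belongs in the 2-hour pot instead.

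A patient in that position has to short one of them, and both matter. The 24-hour weight is a primary variable. The sputum neutrophil count is another, and Section 13.2 makes the 2-hour sample the primary sample for its analysis. If the spot samples are given as instructed, the 24-hour weight is too low.

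Whether this happens depends on each patient's visit dates, so it can occur at baseline, at Visit 4, at both or at neither. When it occurs at only one of them, the change score contains a shift that has nothing to do with treatment. Sputum weight that was never recorded cannot be recovered at the analysis stage.

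**Working it through.** The protocol states no figure to reproduce here. The check sets the windows side by side and then sizes the diverted amount.

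**Step 1: which permitted schedules overlap**

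| 24-hour collection leads to | It starts on rising | Sampling visit that may fall on that day | Permitted? |
|---|---|---|---|
| Visit 1a | day before 1a | none; no earlier sampling visit exists | no overlap |
| Visit 1b | day before 1b | Visit 1a | yes, 24 hours is enough |
| Visit 4 | day before Visit 4 | Visit 3b | yes, no minimum gap is set |

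Overlap therefore needs one of two schedules: 1a the day before a 1b that ends the baseline collection, or 3b the day before Visit 4. Exposure is uneven. A baseline collection tied to 1a is never at risk, while the single end-of-treatment collection is at risk whenever 3b is the day before.

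**Step 2: which pots fall inside the window**

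The spot sample is taken on waking and the 24-hour collection starts on rising, so the waking pot may already be filled when the window opens. The 2-hour collection follows the waking sample and falls inside the window. Only the 2-hour pot is counted below.

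The waking sample on the visit day itself sits at the end of the window, and the text does not say whether it counts. That applies equally at both time points, so it is not part of this point.

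**Step 3: share of the day's output diverted**

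Inputs: 2-hour sample of at least 1 to 2 g (Table 3, footnote i); entry minimum "spontaneously producing an average of 3 ml or more sputum on a daily basis" (Section 5.1). Assumptions: 1 g/mL; daily outputs above the minimum are illustrative, since the protocol gives no typical value.

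Share = diverted grams ÷ true 24-hour grams.

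| True daily output | 1 g diverted | 2 g diverted |
|---|---|---|
| 3 g (entry minimum) | 1/3 = 33% | 2/3 = 67% |
| 10 g (assumed) | 1/10 = 10% | 2/10 = 20% |
| 20 g (assumed) | 1/20 = 5% | 2/20 = 10% |

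**Step 4: effect on the change score**

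Take a patient whose true output is constant at 10 g/day, with 2 g diverted:
- Overlap at Visit 4 only: (8 − 10)/10 = −20%.
- Overlap at baseline only: (10 − 8)/8 = +25%.
- Overlap at both, same amount: (8 − 8)/8 = 0%.

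The distortion comes from overlap at one time point without the other.

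**The case against.** The strongest reply is that the protocol never requires visits on consecutive days. Visits 1a and 1b may fall anywhere within 7 days of Visit 2, and 3a and 3b anywhere within 7 days of Visit 4. The number of patients affected could be zero. At baseline a site can already avoid the problem by using Visit 1a, and Section 7.4.1.2 expects staff and patient to agree in advance how the collection is returned. All of this stands. It makes the problem conditional but does not remove it, because no instruction steers sites away from the overlapping dates and the Visit 4 collection has no alternative visit.

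A reader might infer more than the text supports, in three ways:
- **That the weight is under-measured as a rule.** It is so only on the two schedules above.
- **That one to two thirds of the sputum is typically lost.** That is the worst case, for a patient at the 3 mL entry floor. At higher outputs the share is much smaller, and similar losses at both time points largely cancel.
- **That the treatment comparison is biased.** The trial is randomised and double-blind, so visit spacing should not depend on arm. What remains is noise and false change within patients.

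The study is also exploratory, with several primary variables, and its sample-size illustration uses sputum neutrophils, not weight. That limits the consequence. Some sputum handling is left to a laboratory manual that is not shown, but Section 7.4.1.2 does not refer to that manual for the weight.

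**Conclusion.** The point holds in conditional form. On two schedules that Table 3 and footnote a allow, footnotes h and i cannot both be met, and the 24-hour sputum weight may be too low at one time point and not the other.

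Where that happens, the 2-hour pot alone takes 33–67% of the day's output in the worst case, 10–20% at 10 g/day and 5–10% at 20 g/day. These figures rest on 1 g/mL and on assumed outputs above the entry minimum. They would be larger if more than 2 g is collected or if the waking pot also falls inside the window. The documents do not show how many patients would be scheduled this way.

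The consequence is avoidable measurement noise and spurious within-patient change in a primary variable, with 20 patients per group. No systematic difference between arms is shown. It is worth correcting because prevention is cheap and the lost weight cannot be reconstructed afterwards.

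**What to change.** State in Table 3, footnotes a and h, that no visit with waking and 2-hour samples may fall on the day a 24-hour collection starts. In practice:
- **Baseline:** tie the collection to Visit 1a, or place Visit 1b at least 2 days after Visit 1a.
- **End of treatment:** place Visit 3b at least 2 days before Visit 4.

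Both fit inside the existing 7-day windows. The cost is a line of text in two footnotes and slightly less freedom in booking visits.

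Weighing the separate pots and adding them back is not recommended. Those pots may go directly to the processing laboratory, whereas site staff weigh the 24-hour collection. An add-back would therefore need extra weighing and recording steps, and the variable would be derived differently in different patients.

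While the baseline visit is being fixed, Section 12.2.2 should be aligned with it. It takes the baseline weight from Visit 2, where Table 3 schedules no 24-hour collection.

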4.2 Rationale for study design, doses and control groups

The rationale for conducting this study in patients with bronchiectasis and the rationale for dosing up to 28 days are given in Section 2.3. A parallel group rather than a cross over design is considered more appropriate, as the possible duration of effect is uncertain and therefore a carry-over cannot be completely eliminated. The rationale for dose selection is given below.

The first-in-man, two-part, single and multiple ascending dose (SAD and MAD) study of AZD9668 in healthy volunteers (D0520C00001) is now complete and the reporting phase is underway. In the SAD part of the study the doses that have been safely administered were 2, 10, 30, 60, 120 and 150 mg. Dose escalation was stopped because the exposure limits set by the internal AstraZeneca Human Exposure Limits Committee (HELIC) were reached. These limits (i.e. $AUC_{(0-24h)}$ and C_{max} of 18 $\mu M \cdot h$ and 2.5 μM , respectively) were set following a review of the data obtained in the 1-month toxicology studies in the rat and dog and have been based upon the exposures at the no observed adverse effect level (NOAEL) in rat (370 mg/kg), corrected for the differences in plasma protein binding between the species. The NOAEL in the rat has been used because the free exposures at this dose are lower than those obtained in the dog at the no observed effect level (NOEL) dose. In the MAD part of the study the doses that have been safely administered were 30, 70 and 120 mg once a day for a total of 8 days.

Following single dose administration of AZD9668 (2 - 150 mg) absorption was rapid, median t_{max} ranged from 1 to 2 hours. The geometric mean CL/F ranged from 15.4 to 21.6 L/h and the geometric mean V_z/F ranged from 157 to 334 L. The geometric mean terminal half-life of AZD9668 ranged from 5.04 to 14.99 h. The CL/F, V_z/F and $t_{1/2}$ appeared to be independent of dose. The exposure (C_{max} and AUC) increased proportionally with dose between doses of 10 mg and 150 mg.

AZD9668 is renally eliminated and renal clearance (CL_R) and the percentage of the dose excreted as unchanged AZD9668 in the urine over 48 h ($F_{e(0-48)}$ (%)) appeared to be independent of dose. The geometric mean CL_R ranged from 5.83 L/h to 6.98 L/h, and the range of the geometric mean $F_{e(0-48)}$ (%) was 31.6% to 40.0%.

Following multiple dose administration of AZD9668 (30 mg, 70 mg and 120 mg, once a day for 8 days), absorption was similar following single and multiple dosing; the median t_{max} and $t_{max,ss}$ was 1 hour for all dose groups. The geometric mean $CL/F_{,ss}$ was 14.7, 14.8 and 19.4 L/h and the geometric mean $V_z/F_{,ss}$ was 191L, 218 and 245L, respectively. The geometric mean $t_{1/2,ss}$ was 9.04 hours, 10.24 hours and 8.73 hours, respectively, and there was no evidence for time or dose dependent change in PK. There was no evidence of accumulation upon multiple dosing to steady state.

AZD9668 is renally eliminated and renal clearance at steady state ($CL_{R,ss}$) and the percentage of the dose excreted as unchanged AZD9668 in the urine at steady state over 48 hours ($F_{e(0-48),ss}$ (% dose)) appeared to be independent of dose. The geometric mean $CL_{R,ss}$ was 5.29 L/h, 5.70 L/h and 5.83 L/h, and the geometric mean $F_{e(0-48),ss}$ (% dose) was 38.8%, 40.9% and 31.6%, respectively.

Administration of AZD9668 after consumption of a high fat meal resulted in a reduction in the rate of absorption (median t_{max} was 4 h, 3 h and 4 h for 30 mg, 70 mg and 120 mg, respectively). The C_{max} was reduced by 22 %, 31 % and 22 % and the $AUC_{(0-24h)}$ was slightly reduced, by 8%, 5% and 5% for 30 mg, 70 mg and 120 mg, respectively. Thus consumption of the food reduced the rate but had relatively little effect on the overall extent of absorption.

A population PK model of the PK data from the SAD and MAD study has been developed and was used to estimate the mean population PK parameters of AZD9668 with the associated variability and to assess the affect of consumption of a high fat breakfast on the PK of AZD9668. A dose of 60 mg twice a day has been selected as the dose for the current study. This dose has been chosen as a dose that is predicted to achieve trough steady state therapeutic plasma concentrations of 19 nM (predicted from an in vivo mouse acute lung injury model) in all patients, whilst ensuring that the predicted geometric mean $C_{max,ss}$ and $AUC_{(0-24h),ss}$ are below the HELC limits. The estimated margins to the HELC limits in the fasted state are 2.6 and 1.4 for $C_{max,ss}$ and $AUC_{(0-24h),ss}$, respectively.

From the population PK modelling it was identified that the bioavailability of AZD9668 was approximately 90% of that when it was administered in the fasted state. This did not however have any impact upon the dose selection for the subsequent studies therefore it is not necessary for the patients to restrict food around administration of their doses.

All doses will be administered with approximately 100 mL water. There is no requirement to restrict food consumption before or immediately after administration of AZD9668 except for the morning dose on Days 1 and 28 (Visits 2 and 4, respectively) where an ECG is being performed around t_{max} .

Rationale for the optional pharmacogenetics component of the study is included in Appendix D.

